Endpoint(s)	
Primary outcome:
 
 Good functional outcome 6 months after treatment, measured by the mRS. Good functional outcome is defined as a mRS of ≤ 3 points and will be assessed as binary outcome (yes/no, final value) at 6 months (blinded) after treatment. The cut-off for good functional outcome is chosen at a mRS score of 3 points, as this reflects the turning point for a patient being able to live a partially self-dependent life or to live a severely disabled life. In this context, a mRS score of 3 points reflects the ability to walk unassisted and care for one's own bodily needs despite being moderately dependent on assistance, while a mRS score of 4 points describes a patient who is not able to walk anymore and needs assistance with all daily activities and thus marks a severe loss of patient autonomy. 
Secondary outcomes:
 
 The mortality rate as measured by death of a participant (binary outcome (yes/no), final value) at 6 months after intervention. Patient reported outcome measures at 7 days (Patient satisfaction and cognition), 3 and 6 months after intervention, those being: 
 Patient and caregiver quality of life as assessed by the PROMIS[®] questionnaire (continuous variable, final value) Patient Satisfaction as assessed by a short survey (Appendix 2) on a scale of 1-5 (continuous variable, final value) Patient cognitive outcome as assessed by the MOCA[®] Test (continuous variable, final value) The morbidity rate, meaning occurrence of: 
 Ischemic stroke Recurrent SSICH (defined as any radiologically confirmed increase in hematoma volume postoperative/follow-up that is either asymptomatic or associated with a worsening of the focal-neurological deficit by ≥ 4 points on the NIHSS and/or a decrease in consciousness by ≥ 2 points on the GCS) Epileptic seizure Surgical site infection (intervention group only) Any need for open neurosurgical procedures Infections (i.e. pneumonia, urinary tract infection) Any other not defined complication that prolongs the hospital stay and/or leads to further treatment not envisaged in the original treatment plan. 
The occurrence of any of these events 6 months after intervention (binary variable (occurrence/no occurrence), final value, proportion).
 
 The change of focal neurological deficit measured by the NIHSS, from baseline to 6 months after intervention as a continuous variable (continuous variable, change from baseline). The time to intervention, defined as the period from symptom onset/last seen well to start of surgery (start surgical measures, i.e. positioning of patient) or start of medical treatment (admission of first treatment of BMT) (continuous variable, time to event).

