- The change of disability measured by the mRS, from baseline to 6 months after intervention as a continuous variable (change from baseline, so called mRS shift analysis).
- The time to intervention, defined as the period from symptom onset/last seen well to start of surgery (start surgical measures, i.e. positioning of patient) or start of medical treatment (admission of first treatment of BMT) (continuous variable, time to event).
- The temporal evolution of serum levels of the prespecified biomarkers as continuous variable from start to 6 months after intervention (continuous variable, change from baseline).
- The total time spent on the intensive care unit (ICU)/stroke unit as a continuous variable from the first admission to the ICU/stroke unit to discharge from ICU/stroke unit at 7 days/discharge after intervention (continuous variable, final value).
- The total time spent in intubation measured in minutes from the start of intubation to extubation as specified in the anesthesiology report at 7 days/discharge after intervention (continuous variable, final value).

Outcomes/Measurements applying to the intervention group only:

- The proportion of hematoma volume reduction rate (goal $\leq 15\%$ of its initial volume). The hematoma volume will be measured on serial cranial computer tomography (cCT) and the difference between the volume of the cCT used for surgery and the cCT directly after surgery will be calculated. The hematoma volume on the pre-

operative cCT will be calculated using the $(A * B * C)/2$ method during screening and secondarily validated using the volumetric function of the navigation software[34] Hematoma on directly postoperative images will be calculated using the volumetric function of the navigation software. The hematoma volume reduction rate will be a binary variable (achieved reduction < 15%/did not achieve reduction < 15%, final value).

- The relative (percentage) reduction or increase of hematoma volume from baseline admission cCT to postoperative cCT directly after surgery as a continuous variable (final value).

Additionally, we will collect baseline data of all patients such as age, sex, prior medical history and medication out of the electronic patient file.

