3.4 Study intervention

3.4.1 Intervention group

The intervention group will first receive BMT (as described below) upon admission and early minimally invasive image guided endoscopic hematoma evacuation as an add-on therapy to BMT. Surgery will be performed within 6-24 hours after SSICH symptom onset. A detailed standardized presentation of the technique and all critical steps of the surgery including imaging, setup of image guidance and endoscopic equipment, as well as the exact process of aspirating the clot will be provided to all involved surgeons by a proctored workshop. Additionally, we published a technical note describing the technique with a video illustrating the steps of the surgery[37]. All individual parts of the procedure are standard neurosurgical practice. Regular training will be conducted to maintain and improve adherence.

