3.4.2 Control group

The control group will receive the current gold standard treatment for SSICH according to the guidelines (BMT)[12]. This involves strict blood pressure control (SBP<140mmHg), if needed with intravenous or intraarterial blood pressure lowering agents, reversal of anticoagulation if applicable, intensive care surveillance and nursing on a ICU or stroke unit, control of seizures as well as glucose levels as needed and neurointensive monitoring if deemed necessary[12].

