4.3.1 V1: Study inclusion, baseline assessment and treatment: up to 24 hours after symptom onset

Study eligibility criteria are confirmed and written informed consent is obtained from the patient. After informed consent was given, randomisation to the intervention or the control group will be conducted by a member of the study team through the CDMS SecuTrial®.

A clinical examination is performed including vital signs (resting blood pressure and heart rate, height, and weight), NIHSS, GCS, and mRS. Blood sampling for biomarkers will be obtained. Patient baseline data is acquired.

In the intervention group a study baseline CT scan (stability scan) is obtained 6 hours after the admission scan if surgical hematoma evacuation is started >6 hours after the admission scan. Endoscopic hematoma evacuation must be initiated within 24 hours according to the procedure described in 3.4.1 “Intervention group”. Surgical Baseline data is acquired.

Patients randomised to the control group will receive standard medical care according to the current guidelines as described in 3.4.2 “control group”.

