5.1.3 Planned statistical methods

The primary analyses are performed following the intention-to-treat principle. Additionally, per-protocol analysis will be performed for sensitivity analysis. We study the ratio of positive outcomes in both study arms by performing a Bayesian A/B test after every 40 additional patients, using the method described by Gronau et al.[53]. Data collection (and the periodical analysis of these data) will continue until a Bayes Factor of 10 (or 1/10) is achieved. The odds

ratio and its 95% credible interval will be reported. Covariates ICH volume, presence of intraventricular bleeding, do-not-resuscitate orders, location of hematoma and centre will be included in a Bayesian logistic regression model

Secondary analysis is performed on the secondary outcomes. For continuous variables, a Bayesian regression with normal error term is used, for time-to-event outcomes Bayesian cox-regression is used, and for binary variables Bayesian logistic regression is used. Statistical analysis is performed with R version 4.2.1 or higher (R core Team, 2022)[54]. A complete mRS shift analysis will be calculated.

In parallel to the Bayesian primary analysis, we will perform a frequentist test of proportions comparing study arm for the first 100 patients per study arm. In the ES arm, a number of explorative analyses are performed, studying the relation between hematoma location, hematoma size, and treatment outcome. In particular, for parameters measured over time, figures are created illustrating the development over time at both the patient level and group level.

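### Time to intervention is a both-arm secondary outcome that stops at surgery in one arm and at first medical treatment in the other, so a between-arm analysis mainly reflects its definition

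*Protocol*

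**What the plan says.** Protocol 3.2 and the synopsis define the outcome in the same way: "The time to intervention, defined as the period from symptom onset/last seen well to start of surgery", with first medical treatment as the alternative stopping point. The full stopping rule in 3.2 is "start of surgery (start surgical measures, i.e. positioning of patient) or start of medical treatment (admission of first treatment of BMT". The outcome is tagged both as a continuous variable and as time to event. It stands among the general secondary outcomes, ahead of the separate list reserved for the intervention group.

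On treatment, 3.4.1 says: "The intervention group will first receive BMT (as described below) upon admission". Surgery is added to that. For controls, 3.4.2 says: "The control group will receive the current gold standard treatment for SSICH according to the guidelines (BMT".

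On analysis, 5.1.3 applies secondary analysis to the secondary outcomes and chooses the model by data type. Continuous variables get a Bayesian regression with normal errors, and "for time-to-event outcomes Bayesian cox-regression is used".

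Nothing in the protocol restricts this outcome to one arm, calls it descriptive, or names one event common to both arms.

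**The concern.** The clock starts at the same point in both arms but stops at different steps of care. An ES patient treated as 3.4.1 describes has already had the event that stops a control patient's clock, and the ES clock then runs on to a second, later step. The ES times are longer by construction.

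At stake is a reported secondary result in which ES patients appear to be treated later than controls when their medical treatment began equally fast. The one comparison that could be informative, whether background medical care started equally early in both arms, cannot be made from this outcome, because the ES arm's time to BMT is not part of it.

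**Working it through.** **Inputs from the protocol.** The stopping events and clock start come from 3.2, the order of treatment in the ES arm from 3.4.1, and the models from 5.1.3. The sample sizes are 40 per arm (minimum before the first test), 75 per arm (expected stopping point) and 100 per arm (maximum), from 5.1.2.6 and 4.1. The protocol gives no expected times, effect or power for this outcome, so there is no figure of its own to reproduce.

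**Which model applies.** Mortality and morbidity are tagged binary. ICU and intubation times are tagged continuous, final value. Time to intervention is the only outcome tagged time to event, so if the Cox sentence in 5.1.3 applies to any listed outcome, it applies to this one. Because the tag also says continuous, normal-error regression cannot be excluded.

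**Algebra.** Let B be the time from onset or last seen well to the first BMT measure, and D > 0 the time from that measure to surgery.

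- Control: T_C = B.
- ES: T_E = B + D.
- If BMT timing has the same distribution in both arms, mean(T_E) − mean(T_C) = mean(D). A normal-error regression then estimates the mean delay to surgery.
- If BMT timing differs between arms by δ, the contrast is δ + mean(D), and this outcome cannot separate the two terms.
- Because B + D > B, ES is later at every point of the distribution, so a Cox hazard ratio also falls below 1.

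**Simulation.** There were 2,000 trials per scenario, with all times observed and B drawn from the same distribution in both arms. The test was a two-sided 5% log-rank test (the Cox score test), used as a frequentist stand-in for the Bayesian Cox model:

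z = Σ(aᵢ − pᵢ) / √Σpᵢ(1 − pᵢ), rejecting if |z| > 1.96,

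where aᵢ marks an ES event and pᵢ is the share of ES patients still at risk. The largest Monte Carlo standard error is √(0.25/2000) = 1.1 percentage points.

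Assumptions not in the documents: BMT start is uniform over 1-6, 1-12 or 1-20 h. Surgery follows BMT by a fixed 1, 2 or 4 h, or is uniform from the later of 6 h and BMT + 1 h up to 24 h.

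Trials rejecting, with identical BMT timing:

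| Stopping event in ES | BMT start | 40/arm | 75/arm | 100/arm |
|---|---|---|---|---|
| First BMT measure (common event) | all three | 4.6-6.2% | 5.8-5.9% | 4.6-5.9% |
| Surgery, BMT + 1 h | 1-6 h | 91.1% | 99.8% | 100% |
| | 1-12 h | 39.1% | 65.1% | 80.2% |
| | 1-20 h | 17.4% | 31.7% | 40.6% |
| Surgery, BMT + 2 h | 1-6 h | 100% | 100% | 100% |
| | 1-12 h | 86.8% | 98.9% | 99.9% |
| | 1-20 h | 46.9% | 75.9% | 87.6% |
| Surgery, BMT + 4 h | 1-6 h, 1-12 h | 100% | 100% | 100% |
| | 1-20 h | 92.8% | 99.9% | 100% |
| Surgery spread up to 24 h, none before 6 h | all three | 100% | 100% | 100% |

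Approximate hazard ratios (observed over expected) are 0.99-1.00 with a common event, 0.51-0.79 with a 1 h gap, 0.20-0.50 with a 4 h gap, and 0.18-0.30 with surgery spread up to 24 h. In the last case the median gap is 8.5-11.6 h. Whenever the stopping events differ, the difference points towards ES being later.

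**The case against.** The strongest reply is that the protocol never says this outcome is compared between arms. Section 5.1.3 only matches models to data types, and a statistical analysis plan not shown here could make the measure descriptive. It appears in none of the stated secondary objectives and has no hypothesis, threshold or success rule. A report that surgery began later than medical treatment would be true and self-explanatory. This stands in part: the between-arm Cox analysis is an inference, and the rejection rates show how far the two distributions separate, not a false conclusion the trial is bound to draw. It does not remove the mismatch, which the protocol writes into the definition twice and which a later plan could cure only by departing from it.

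Three stronger readings may tempt a reader, and the documents do not support them.

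- **That a difference appears however the trial runs.** With a 1 h gap and widely spread BMT start, most simulated trials do not reject, even at 100 per arm.
- **That the arms separate completely, leaving a Cox estimate set by its prior.** That needs every BMT start before 6 h and every surgery after it. The clock can start at last seen well and patients can enter up to 24 h, so this is an extreme case. The 6 h lower limit is itself not uniform: 3.4.1 has "Surgery will be performed within 6-24 hours after SSICH symptom onset", while 4.3.1 has "Endoscopic hematoma evacuation must be initiated within 24 hours" with no lower limit. Those passages need reconciling, but the point does not depend on which one stands, since the fixed-gap scenarios use no lower limit.
- **That onset-to-surgery time is lost.** It is recorded for ES patients who are operated on and can be summarised within that arm. What the definition leaves out is their time to first BMT measure.

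**Conclusion.** The point holds as a fault of definition. The outcome is listed for both arms, stops at a different event in each, and under the treatment sequence in 3.4.1 the ES time contains the control arm's event plus a further delay. A between-arm analysis, whether Cox or normal-error, would mainly reflect that construction.

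How visible the artefact would be depends on times the documents do not give. Under the assumptions above it is near certain to show when surgery follows BMT by about 4 h or more, and uncertain when the gap is about 1 h and BMT start is widely spread. Its direction does not change.

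Severity is low. This is one secondary process measure, and the primary analysis is not affected.

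**What to change.** In 3.2 and in the synopsis endpoints, replace the single outcome with two:

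1. Onset or last seen well to first BMT measure, recorded as the same event in both arms and compared between arms as a check on equal background care.
2. Onset or last seen well to start of surgery, moved to the list of measurements for the intervention group only and reported descriptively, for example as median and interquartile range.

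State that surgery start in the ES arm is not compared with BMT start in the control arm.

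The cost is a change of wording and one timestamp in the ES arm's case report form, for an event that already occurs in routine care. No patients or procedures are added. The price is that one listed two-arm comparison becomes descriptive.

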Statistical Considerations	
The primary analyses are performed following the intention-to-treat principle. Additionally, per-protocol analysis will be performed for sensitivity analysis. We study the ratio of positive outcomes in both study arms by performing a Bayesian A/B test after every 40 additional patients, using the method described by Gronau et al.. Data collection (and the periodical analysis of these data) will continue until a Bayes Factor of 10 (or 1/10) is achieved. The odds ratio and its 95% credible interval will be reported.
 
Secondary analysis is performed on the secondary outcomes. For continuous variables, a Bayesian regression with normal error term is used, for time-to-event outcomes Bayesian cox-regression is used, and for binary variables Bayesian logistic regression is used adjusted for covariates. Statistical analysis is performed with R version 4.2.1 or higher (R core Team, 2022).
 
In parallel to the Bayesian primary analysis, we will perform a frequentist test of proportions comparing study arm for the first 100 patients per study arm. In the ES arm, a number of explorative analyses are performed, studying the relation between hematoma location, hematoma size, and treatment outcome. In particular, for parameters measured over time, figures are created illustrating the development over time at both the patient level and group level.

Inclusion- / Exclusion Criteria	
Inclusion criteria:
 
 Patient age ≥ 18 and < 85 Spontaneous supratentorial intracerebral hemorrhage (SSICH), defined as the sudden occurrence of bleeding into the lobar parenchyma and/or into the basal ganglia and/or thalamus that may extend into the ventricles confirmed by imaging SSICH volume ≥ 20 mL < 100 mL (measured using the formula $\frac{A * B * C}{2}$) Stable clot volume defined as absence of increase of $> 33\%$ (as assessed using the formula $(A * B * C)/2$) of initial clot volume on follow-up imaging. A focal neurological deficit consisting of either 
 clinically relevant hemiparesis (≥ 4 motor points on the NIHSS for facial palsy, motoric upper and lower extremities combined)

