Number of Participants with Rationale	
Based on the to-date available literature, our own meta-analysis and the data of 2020-2022 derived from the Swiss stroke registry we assume a favorable outcome around 50% for patients treated with BMT, while we anticipate a positive risk ratio of 1.6 towards favorable outcome for ES compared to BMT. Based on these assumptions, we explored sample sizes needed for achieving “compelling evidence”, as described by Schönbrodt & Wagenmaker.
 
Systematic reviews as well as data analyzed from the Swiss Stroke Registry over the last 2 years suggests that a plausible assumption for the proportion of positive outcomes in the control arm is 50% (0.5). Based on our calculations after collecting data of 70 patients per study arm, about 90% of trials will have achieved a BF of 10, being the “Bayesian equivalent” to a power of 90%. In addition, 50% of the simulated trials already achieve this level of evidence after the 40th hypothetical patient (per arm). Further, based on these calculation, it is extremely unlikely that the trial would take more than 130 patients per arm. Based on these results we assume that we will likely be able to stop collecting data before reaching 75 patients per arm (total of 150 patients) to reach a BF of 10.

Study Intervention	Early minimally invasive image guided endoscopic hematoma evacuation as an add-on therapy to BMT performed within 24 hours after SSICH symptom onset.
Control Intervention	Best medical treatment i.e. active blood pressure control, seizure prophylaxis and care as according to the current guidelines.
Study procedures	6 Visits in total, 4 of them during hospital stay, 2 of them as follow-up visits within the clinical routine. Each visit consists of assessing GCS, mRS and NIHSS, three visits include CT scans (before intervention, directly postoperative and during follow up) and blood sampling (before intervention, postoperative and during follow up). Three visits include assessing patient satisfaction and cognition, and two visits include patient quality of life assessments.
Study Duration and Schedule	
Estimated duration for the main investigational plan is estimated to last 5 years
 
Planned 09/2023 of First-Participant-In Planned 09/2028 of Last-Participant-Out

Investigator(s)	
Principal Investigator: PD Dr. med. [name] Senior Neurosurgeon, Head of Clinical Research Department of Neurosurgery, University Hospital Basel

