3 STUDY OBJECTIVES AND DESIGN

3.1 Hypothesis, primary and secondary objectives

The **Null hypothesis (H₀)** describes no difference in functional outcome rates of early minimally invasive image-guided endoscopic evacuation additionally to BMT for SSICH compared to BMT alone.

The **Alternative Hypothesis (H₁)** describes a difference (either improved or worsened [two-sided testing]) functional outcome rates of early minimally invasive image guided endoscopic evacuation additionally to BMT for SSICH compared to BMT alone.

The primary objective of this two, armed, open-labelled, single centre randomised controlled trial is to show superiority of early minimally invasive image-guided hematoma evacuation additionally to BMT compared to BMT alone in functional outcome rates at 6 months in patients with SSICH.

Secondary objectives are:

- to show superior survival rates of patients in the ES arm
- to study patient reported quality of life after treatment for SSICH at different time points (3 and 6 months after intervention)
- to study patient satisfaction with the outcome after treatment for SSICH at different time points (3 months and 6 months after intervention)
- to study cognitive outcome in patients after treatment for SSICH at different time points (3 months and 6 months after intervention)
- to study the morbidity rates of patients in both treatment arms
- to study the efficacy of ES in reducing the hematoma volume
- to study the change in focal neurological deficits exhibited by the patients after treatment.
- to study the temporal evolution of serum biomarkers (Neurofilament light-chain subunit (NfL), Glial Fibrillary Acidic Protein (GFAP), S100 calcium-binding protein B (S100B), IL-1 α and β , IL-2, IL-4, IL-5, IL-6, IL-8, IL-10, IL-12p70 and TNF- α) and their change in relation to early hematoma ES.

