3.2 Primary and secondary outcomes

Primary outcome:

- Good functional outcome 6 months after treatment, measured by the mRS[33]. Good functional outcome is defined as a mRS of ≤ 3 points and will be assessed as binary outcome (yes/no, final value) at 6 months after treatment. The cut-off for good functional outcome is chosen at a mRS score of 3 points, as this reflects the turning point for a patient being able to live a partially self-dependent life or to live a severely disabled life. In this context, a mRS score of 3 points reflects the ability to walk unassisted and care for one's own bodily needs despite being moderately dependent on assistance, while a mRS score of 4 points describes a patient who is not able to walk anymore and needs assistance with all daily activities and thus marks a severe loss of patient autonomy.

Secondary outcomes:

- The mortality rate as measured by death of a participant (binary outcome (yes/no), final value) at 6 months after intervention.

- Patient reported outcome measures at 3 and 6 months after intervention, those being:
 - Patient and caregiver quality of life as assessed by the PROMIS® questionnaire (continuous variable, final value)
 - Patient Satisfaction as assessed by a short survey (Appendix 2) on a scale of 1-5 (continuous variable, final value)
 - Patient cognitive outcome as assessed by the MOCA® Test (continuous variable, final value)
- The morbidity rate, meaning occurrence of:
 - Ischemic stroke
 - Recurrent SSICH (defined as any radiologically confirmed increase in hematoma volume postoperative/follow-up that is either asymptomatic or associated with a worsening of the focal-neurological deficit by ≥ 4 points on the NIHSS and/or a decrease in consciousness by ≥ 2 points on the GCS)
 - Epileptic seizure
 - Surgical site infection (intervention group only)
 - Any need for open neurosurgical procedures
 - Infections (i.e. pneumonia, urinary tract infection)
 - Any other not defined complication that prolongs the hospital stay and/or leads to further treatment not envisaged in the original treatment plan.

The occurrence of any of these events 6 months after intervention (binary variable (occurrence/no occurrence), final value, proportion).

- The change of focal neurological deficit measured by the NIHSS, from baseline to 6 months after intervention as a continuous variable (continuous variable, change from baseline).

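### The protocol defines the biomarker and NIHSS outcomes as change from an acute baseline but does not provide for the patient's own baseline value as a covariate or state a scale for the concentrations

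*Protocol*

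**What the plan says.** Section 3.2 gives most outcomes a metric. For the biomarkers it is "from start to 6 months after intervention (continuous variable, change from baseline". For NIHSS it is "The change of focal neurological deficit measured by the NIHSS, from baseline to 6 months after intervention", also continuous and also tagged as change from baseline. PROMIS and MOCA are tagged as final values, so the change form was chosen outcome by outcome.

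On the model, section 5.1.3 says: "For continuous variables, a Bayesian regression with normal error term is used". It names no covariates for these models and no transformation.

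Baseline factors are named in three places:
- The end of 3.2 lists age, comorbidities and oral anticoagulants as possible confounders or effect modifiers. It then gives the corrections for the primary outcome.
- Section 5.1.3 says: "Covariates ICH volume, presence of intraventricular bleeding, do-not-resuscitate orders, location of hematoma and centre will be included in a Bayesian logistic regression model". This stands in the primary-analysis paragraph.
- Section 5.1.5 repeats those five factors for the exploratory subgroup analyses.

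The visit 1 biomarker or NIHSS value is in none of them. The synopsis sentence on secondary analyses ends "for binary variables Bayesian logistic regression is used adjusted for covariates", without a list.

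The data needed are already collected. The synopsis describes "blood sampling (before intervention, postoperative and during follow up", and the schedule places sampling at visit 1 (within 24 hours of onset), visit 3 (72 hours) and visit 6. NIHSS is taken at every visit.

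**The concern.** Visit 1 falls within the first day of a brain haemorrhage. It is plausible, though not documented here, that concentrations then differ far more between patients than they do six months later. An unadjusted change score subtracts the whole baseline value, so all of that acute scatter enters the outcome, and a chance difference between arms at visit 1 passes straight into the estimated effect. Adjusting for baseline removes only the part of the baseline that predicts the 6-month value.

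At stake is the precision of two secondary objectives: the change in neurological deficit, and the change in 13 biomarkers (NfL, GFAP, S100B, nine interleukins and TNF-α) in relation to early evacuation. For concentrations the scale matters too. On the original scale, a few very high acute values can dominate an absolute change.

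**Working it through.** **Is there a figure in the plan to reproduce?** Not for these outcomes. The protocol gives no effect size, SD, correlation or power for any biomarker or for NIHSS. Its only power figure, about 90% at 70 patients per arm, concerns the binary primary outcome and does not enter here.

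**Inputs (all assumed).** Let the 6-month SD be 1, k the baseline SD divided by the 6-month SD, and ρ the correlation between the two values. I use ρ from 0.2 to 0.8 and several values of k. Power at a two-sided 5% level serves only as a yardstick for precision, since the trial's analysis is Bayesian.

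**Variances within an arm.**
- Unadjusted change: 1 + k² − 2ρk
- Adjusted for baseline: 1 − ρ²
- Difference: (1 + k² − 2ρk) − (1 − ρ²) = (k − ρ)²

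The difference is never negative, so the change score is never the more efficient of the two. It is zero exactly when k = ρ.

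**Power.** Let R = (1 + k² − 2ρk) / (1 − ρ²). If the adjusted analysis has 80% power, the unadjusted change has power Φ((1.960 + 0.842)/√R − 1.960). In this normal approximation the number of patients cancels, so no survivor count has to be assumed.

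| k | ρ | R | Power of unadjusted change |
|---|---|---|---|
| 1 | 0.2 | 1.6/0.96 = 1.67 | Φ(0.21) = 58% |
| 1 | 0.8 | 0.4/0.36 = 1.11 | Φ(0.70) = 76% |
| 1.5 | 0.2 | 2.65/0.96 = 2.76 | 39% |
| 2 | 0.5 | 3.0/0.75 = 4.00 | Φ(−0.56) = 29% |
| 2 | 0.8 | 1.8/0.36 = 5.00 | Φ(−0.71) = 24% |
| 0.5 | 0.5 | 0.75/0.75 = 1.00 | 80% (no loss) |

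The loss is therefore 4 to 22 points at equal SDs, about 51 to 56 points at k = 2, and nil where k equals ρ. The change score is also noisier than the 6-month value alone whenever 1 + k² − 2ρk > 1, that is, whenever ρ < k/2.

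**Does the outcome label have to change?** No. Write Y0 and Y1 for the two values and T for arm. The model Y1 − Y0 = a + bT + cY0 is the same as Y1 = a + bT + (c + 1)Y0. The arm effect b is identical on a given scale. In a Bayesian fit this is exact with a flat prior on the baseline coefficient, and a vague prior gives practically the same result.

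**Does the scale matter?** In a simulation with log-normal concentrations (assumed log-SDs 0.5 to 1, ρ 0.2 to 0.7, baseline geometric mean 4.5 times the 6-month one, 55 per arm), the effect was set to give about 80% power for the log value adjusted for log baseline. Absolute change adjusted for the untransformed baseline then had about 54–74% power, give or take a few points. Under these assumptions a covariate without a stated scale recovers only part of the loss.

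**The case against.** The strongest reply is that the protocol is silent rather than wrong. A reader might infer that it plans an unadjusted change on the original scale, but the documents do not say so. The five named covariates belong to the primary analysis. The synopsis mentions adjustment for covariates in its secondary-analysis sentence, although the phrase follows the binary model and may cover only that. Section 5.1.6 refers to a detailed analysis plan that is not shown. A normal error term is compatible with logged values, and a change score is compatible with a baseline covariate. All of this stands. The point is therefore that the protocol does not provide for the adjustment, not that it rules it out.

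A reader might also conclude that much of the power is lost. That depends on k and ρ, which the documents do not give, and the large losses need acute scatter well above 6-month scatter. For NIHSS the case is weaker still: eligibility selects on baseline deficit, and the log-scale argument does not apply.

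Nor does the loss rest on a small count of survivors. Applying the background section's 40–45% mortality to both arms would leave about 55–60 of 100 per arm. The design, however, assumes 50% × 1.6 = 80% with mRS ≤ 3 under surgery, hence at least 80 of 100 alive in that arm.

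Finally, no test or threshold is set for these outcomes, and the protocol also plans figures over time. No stated decision would go wrong.

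What survives is narrower. Section 3.2 fixes the change form and section 5.1.3 the error model, the baseline value appears in no covariate list, and adding it is never less efficient in large samples.

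**Conclusion.** The concern holds as a free improvement to two sets of secondary outcomes. The direction is certain under randomisation: the variance excess of an unadjusted change is (k − ρ)². The size is not known. Against 80% power when adjusted, the unadjusted change has about 58–76% at equal SDs and about 24–29% if the baseline SD is twice the 6-month SD, for ρ between 0.2 and 0.8. It has nearly 80% where the SD ratio is close to ρ. These figures rest on assumed SDs and correlations.

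No stated figure in the protocol is wrong, and the primary analysis is unaffected. The 6-month comparison among survivors is a separate limitation. If surgery changes mortality, survivors are no longer a randomised comparison, and adjusting for baseline does not solve that.

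**What to change.** In section 5.1.3, state that the models for NIHSS and for each biomarker include the patient's own visit 1 value of that outcome as a covariate. State also that biomarker concentrations are analysed on the log scale with the log visit 1 value as covariate, and that arm effects are reported as geometric-mean ratios with 95% credible intervals. NIHSS stays on its own scale.

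The change-from-baseline description in 3.2 may stay, because with baseline in the model the arm effect is the same for change and for the final value on a given scale. Absolute changes can still be shown descriptively.

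The cost is a few sentences and one covariate per model. The samples and scores are already scheduled, so no patient, visit or procedure is added. The small downside is that biomarker effects become ratios rather than absolute changes.
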